Morbidity and burden of childhood nephrotic syndrome: *Idiopathic nephrotic syndrome (NS) is one of the most common chronic kidney diseases in children*, with a prevalence of approximately 16 cases per 100,000 children. NS is characterized by heavy urinary losses of protein leading to hypoalbuminemia, edema, and hyperlipidemia.¹ Children are treated with high-dose corticosteroids on presentation, and >80% respond to treatment with resolution of proteinuria and symptoms. However, 80-90% of the children initially sensitive to corticosteroids will experience disease relapse, with more than half relapsing frequently or becoming dependent on corticosteroids to maintain remission.²⁻⁵ During a relapse, patients can suffer from anasarca, acute kidney injury, serious infections, or thromboembolic events. A cross-sectional analysis of the U.S. Kids' Inpatient Database from the Healthcare Cost and Utilization Project found that NS resulted in an estimated 48,700 inpatient days and charges totaling \$259 million in 2006 and 2009. On average, a single NS hospitalization generated charges of \$26,500. Furthermore, 16% of the hospitalized patients had at least one serious complication, including thromboembolism, septicemia, peritonitis, pneumonia, and diabetes.⁶

Critical issues and barriers to optimal management: Management of children with NS entails long-term outpatient surveillance and treatment. Home care includes the important standard-of-care task of urine monitoring to follow the relapsing-remitting nature of the disease. Caregivers are trained to test the patient's urine routinely with test strips at home. These strips have small blocks of paper impregnated with various reagents that produce visible colorimetric reactions once in contact with urine, which can be interpreted by eye. One reagent block produces a semi-quantitative result for urine protein (Figure 1). New proteinuria signals disease relapse *before* the development of overt symptoms such as edema. Thus, patients are instructed to alert their providers to the occurrence of proteinuria in a timely manner so that corticosteroids can be initiated or adjusted to treat each relapse and prevent acute disease complications. It is also important for the patients to track urine protein for resolution so that

[figure not shown]

Figure 1. Urine test strip with protein reagent block (arrow).

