b) Alerts for significant urine protein findings	
 • Generates alerts to the user for new disease relapse, newly achieved disease remission, or prolonged disease relapse > 2 weeks • Prompts user to send the result to their provider and call their provider 	
 • Self-management support: provides basic information; facilitates disease assessment; emphasizes patient’s central role in care • Clinical information systems: provide timely reminders for patients; summarizes data; shares information with patients
c) Transmission of urine protein results	
 • Generates an auto-populated e-mail with testing results. User indicates with one click that they agree with the transmission. • User can send results at any time through UrApp. 	
 • Clinical information systems: identifies subpopulations for proactive care; facilitates individual patient care planning; shares information with providers to coordinate care • Delivery system design: plans interactions and follow-up individualized to disease severity
d) Urine protein documentation	
 • Results are color coded for an intuitive read: “normal (green)” for “negative/trace,” “moderate (yellow)” for “1+,” and “high (red)” for “2+/3+.” • Displays urine protein results in a line graph as well as by calendar. 	
 • Self-management support: provides basic information; facilitates disease assessment • Clinical information systems: summarizes data, shares information with patients
e) Education materials	
 • Provides documents and videos on: disease complications; importance of urine monitoring; interpretation of urine protein results; how to check urine at home; diet guidelines for children taking corticosteroids; and low sodium diet. 	
 • Self-management support: provides basic information; emphasizes patient’s central role in care; organizes resources to provide ongoing support • Decision support: shares information with patients to encourage their participation

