Demographic characteristics of the patient caregiver (UrApp user) and the patient will be collected from the medical chart and by participant questionnaire. Variables will include: caregiver age, gender, race/ethnicity, income level, and educational level; patient age, gender, and race/ethnicity. As one inclusion criteria for trial participation is ownership of an iPhone, examination of demographic variables will provide information on the representativeness of the cohort to the general NS population and the generalizability of study findings. Baseline self-efficacy and QoL will be assessed by surveys. Caregiver self-efficacy will be assessed by a survey adapted from the Self-Efficacy for Managing Chronic Disease 6-Item Scale (Stanford Patient Education Research Center). The survey will include 3 questions with a scale of 1/not at all confident to 10/totally confident. Patient/caregiver-reported QoL will be assessed by using the 23-item Patient-Reported Outcomes Measurement Information System - Pediatric Quality of Life Inventory (PedsQL). PedsQL was developed as part of the NIH Roadmap Initiative to create universal measures for patient-reported outcomes, and contains questions in the domains of social-peer, depression, anxiety, mobility, and function. The survey has been found to have validity and feasibility in children and adolescents with NS.²² Caregivers and patients ages 5-17 will be surveyed with parent or patient forms, respectively.

2) Outcome measures will be collected at 6 and 12 months via caregiver surveys, medical chart review, and urine protein logs (UrApp data logs for the UrApp arm). We will perform 4 follow-up attempts within a 1-month timeframe to increase survey responses. Adherence to medications will be evaluated via caregiver survey with the validated 4 question Morisky, Green, and Levine (MGL) Adherence Scale.²³ We define adherence as a score of ≥ 3 on the MGL scale. Adherence with urine monitoring will be evaluated with a newly created questionnaire (Figure 4). In addition, UrApp data log (UrApp arm)

- 1) On average in the past month, how often did you check your child's urine for protein? (Once a week, 2-4 times a week, or 5-7 times a week)
- 2) In the past month, have you reduced how often you check your child's urine because he/she is in remission? (Yes or No)
- 3) In the past month, have you increased how often you check your child's urine because he/she is in relapse? (Yes or No)

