Aim 2. In parallel with the pilot trial, perform a mixed-methods process evaluation of the implementation of UrApp to determine the influences on its effectiveness. Process evaluation examines the extent to which an intervention is implemented as intended and the influences on its effectiveness, and is increasingly recognized as integral to both the development and assessment of health promotional programs.²⁴ Our UrApp-based intervention program is novel in the childhood NS field; hence, we will perform process evaluation alongside the pilot RCT to increase the *rigor* of this formative process to design an effective self-management support tool. Aim 2 design is collaboratively developed by [name] and experts in behavioral and implementation sciences, Drs. [name] and [name].

Aim 2a. Evaluate UrApp engagement, use retention, and features used via user analytics and

examine their relationships with UrApp efficacy with respect to primary and secondary outcomes. One of the main purposes of process evaluation is to determine the extent to which an intervention was delivered as intended. Key elements include: *fidelity* (delivery as planned) and *dose* (quantity of the intervention delivered and extent to which participants actively engaged with the materials including initial and continued use).^{24,25} We operationalize these concepts as: UrApp engagement (frequency of use [*dose*]), retention (use over time [*dose*]), and app functions used and frequency of use (depth of use [*fidelity and dose*]).

Procedures and analysis: User behavior data are automatically captured by UrApp analytics and include information on: frequency of use, frequency of use over time, and specific app functions used and frequency. These measures will be downloaded at 6 and 12 months among participants in the UrApp arm (n=30). *A priori*, we define adequate engagement as accessing UrApp at least two times per week during the first 3 months, poor retention as a 50% decrease in weekly use over time, and adequate depth of use as transmission of data to providers for all episodes of disease relapse/remission when prompted. The relationship between user behavior and primary and secondary outcomes (detailed under Aim 1) will be assessed via Chi-square test/Fisher's exact test or t-tests or Wilcoxon rank-sum tests, as appropriate.

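### The all-or-none rule for adequate depth of use in Aim 2a is harder to meet the more a child relapses, so its unadjusted tests against delayed relapse and hospitalization lean toward a spurious protective link

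*Combined protocol and SAP*

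**What the plan says.** Section 2, Study Design, Aim 2a (Procedures and analysis) sets three user-behavior measures in advance for the UrApp arm. The one at issue is "adequate depth of use as transmission of data to providers for all episodes of disease relapse/remission when prompted". The section gives no rule for a family that never has a prompted episode.

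The analysis is a set of two-variable tests: "The relationship between user behavior and primary and secondary outcomes (detailed under Aim 1) will be assessed via Chi-square" or Fisher's exact test, t-tests or Wilcoxon rank-sum tests. No adjustment is stated. The covariates in the Aim 1 analysis paragraph belong to the Aim 1 models and are baseline characteristics.

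Table 1, function (b), states what triggers a prompt: "Generates alerts to the user for new disease relapse, newly achieved disease remission, or prolonged disease relapse > 2 weeks". Section 5 (Potential Device Issues, item 4) adds a prompt at least monthly, but that is not tied to a relapse or remission episode.

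Under Aim 1, Measures/Materials, delayed relapse reporting is judged by chart review for occurrence and frequency, and it can only happen if a relapse happens. Hospitalizations are also taken from the records. Background and Significance says that 80-90% of initially steroid-sensitive children relapse, "with more than half relapsing frequently or becoming dependent on corticosteroids to maintain remission".

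**The concern.** The exposure and two of the outcomes share one driver, the number of relapses. More relapses mean more prompts, and so more chances to miss one and lose the adequate label. More relapses also mean more opportunities for a relapse to be reported late or to end in admission. An unadjusted comparison of adequate with inadequate families therefore partly compares children with few relapses against children with many.

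Aim 2 exists to find what influences the app's effectiveness, and its results go to the Aim 3 stakeholder committee, which plans the app's refinement and a full-scale trial. An artefact here could credit transmission of results with preventing late detection or admission when the difference comes from the disease course.

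**Working it through.** **1. The plan's own figure.** Aim 2a states no power or error rate. The only power in the plan is 82% for the Aim 1 urine-monitoring comparison. With 60 x 0.8 / 2 = 24 per arm and 55% vs 90%, exact enumeration of the two-sided pooled Z-test gives 81.96%, so it is reproduced. It does not bear on this point, but it gives the arm size: 30, or 24 after drop-out.

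**2. Chance of being labelled adequate.** If each prompt is sent with probability q, independently, P(all m sent) = q^m. Assume two prompts per relapse (onset and remission), which fits Table 1. The value of q is not in the documents, so a range is shown.

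| Relapses (prompts) | q=0.70 | q=0.80 | q=0.90 | q=0.95 |
|---|---|---|---|---|
| 0 (0) | 1.00 | 1.00 | 1.00 | 1.00 |
| 1 (2) | 0.49 | 0.64 | 0.81 | 0.90 |
| 2 (4) | 0.24 | 0.41 | 0.66 | 0.81 |
| 3 (6) | 0.12 | 0.26 | 0.53 | 0.74 |
| 6 (12) | 0.01 | 0.07 | 0.28 | 0.54 |

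Sending behavior is identical down each column. The 1.00 for no relapse applies only if unprompted families are counted as adequate.

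**3. Size of the artefact in a null model.** Assumptions, none from the documents: relapses per year are gamma-Poisson with mean 2 and shape 1, so P(k) = (1/3)(2/3)^k; q = 0.80; each relapse is reported late with probability 0.3, regardless of sending. P(adequate given k) = 0.64^k, and (2/3) x 0.64 = 0.4267.

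- Adequate, at least one prompt: mean relapses 1/(1 - 0.4267) = 1.744; late relapses 0.3 x 1.744 = 0.52.
- Adequate, unprompted families included: 0.4267/0.5733 = 0.744; late relapses 0.22. Share of all families: (1/3)/0.5733 = 0.581.
- Inadequate: (2 - 0.581 x 0.744)/(1 - 0.581) = 3.74; late relapses 1.12.

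So the contrast is 0.52 vs 1.12, or 0.22 vs 1.12, while the share of relapses reported late is 30% in every group. In simulated trials of n=30 the Wilcoxon test gives p<0.05 in about 17% with unprompted families excluded and about 77% with them counted as adequate.

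**4. A second null model.** Assumptions: no relapse in 15%, 1-2 in 42.5%, 3-6 in 42.5%; late probability 0.2 or 0.4 and admission probability 0.1 or 0.2 per relapse; q from 0.70 to 0.95; 2000 runs each. Proportion of runs with p<0.05:

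| Comparison | n=30 | n=24 |
|---|---|---|
| Depth vs late relapses, unprompted counted as adequate | 17-76% | 14-63% |
| Depth vs late relapses, unprompted excluded | 9-24% | 7-19% |
| Depth vs hospitalizations, unprompted counted as adequate | 13-41% | 9-30% |
| Share of prompts sent vs share of relapses late, children with a relapse | 4-8% | 5-9% |

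Hospitalization was not run with unprompted families excluded.

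**5. Changing the prompt model.** Starting from step 3, late relapses per family in adequate vs inadequate families:

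| Assumption | Unprompted excluded | Unprompted included |
|---|---|---|
| Late relapses trigger no prompt | 0.65 vs 1.00 | 0.40 vs 1.00 |
| Also, families differ in tendency to delay (beta, mean 0.3) | 0.67 vs 0.76 | 0.52 vs 0.76 |
| Also, less spread in relapses (gamma shape 4) | 0.57 vs 0.51 | 0.65 vs 0.51 |

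In the first row p<0.05 occurs in about 7% of trials at n=30 and 5% at n=24, unprompted families excluded; once families also differ in delay it is close to 5%. Even so, inadequate families average about 3.1-4.0 relapses against 2.1-2.3 in adequate families with a prompt.

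**The case against.** The strongest reply is that the null models treat prompts and delay as unrelated, and the plan does not. The app raises an alert only from results recorded in it, so a relapse discovered at a visit may never have produced a prompt. A transmitted relapse is passed to the physician within 1 business day (Section 5, Safety Monitoring), so sending and timely reporting are linked by design. Step 5 shows that such features can shrink the delayed-relapse gap to almost nothing, or reverse it. The highest rates also come from counting unprompted families as adequate, which the plan does not say. And Aim 2a is a process evaluation in one arm of a pilot; Aim 3 also draws on surveys and interviews.

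All of this stands as a limit on size and certainty. It does not remove the defect: in every variant the rule sorts families by relapse count, the tests ignore that count, and unprompted families have no rule.

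A reader might go further and infer that retention, defined as "poor retention as a 50% decrease in weekly use over time", is driven by relapses too. The documents do not show it. The definition has no relapse term. The questionnaire only asks "have you reduced how often you check your child's urine because he/she is in remission"; it gives no rate, and families are told to test daily. In a simulation with 7 tests a week in relapse, mean relapses in poor vs other retainers were 2.5 vs 2.6 if remission testing was 3 a week and 2.2 vs 2.7 at 2 a week (p<0.05 in 6.5%). Only at 1 a week was the gap marked (1.9 vs 3.4; 25%), and poor retention then went with better outcomes. Nor is it an error that retention and urine-monitoring adherence use different cut-offs, since they are different constructs.

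**Conclusion.** The point holds for depth of use against two outcomes, delayed relapse and hospitalization. The all-or-none rule falls as q^m with the number of prompts, and the unadjusted tests are biased toward a protective link to the extent that these outcomes rise with the relapse count. Under the null models, the false-positive rate for delayed relapse at n=30 runs from about 9% to 24% with unprompted families excluded and from about 17% to 77% with them counted as adequate. It falls close to 5% if late relapses trigger no prompt and families differ in delay. Relapse distribution, sending probability, and delay and admission rates are all assumptions.

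It would be too strong to conclude that engagement in general will look linked to outcome. The engagement measure, "accessing UrApp at least two times per week during the first 3 months", has no relapse term; the retention link is not shown; and nothing in the documents extends the mechanism to adherence, self-efficacy or quality of life. The randomized comparison in Aim 1 is untouched. What is at risk is the interpretation of the process evaluation, so the change is worth making but not critical.

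**What to change.** Amend the Aim 2a analysis wording before the data are examined:

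- Replace the all-or-none depth rule with the proportion of prompted relapse/remission episodes that the family transmitted.
- Exclude families with no prompted episode from the depth analysis, and report how many there are.
- Relate depth to the share of a child's relapses reported late, not to the count or to any occurrence.
- Adjust the hospitalization association for the number of relapses, or stratify by it.
- Report these associations as exploratory, with estimates and intervals.

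In the second null model, the share-against-share analysis brought the false-positive rate for delayed relapse to about 4-9%.

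The inputs are already collected in the app log and the Hospitalizations and Relapses CRF, so no new procedure is needed. The cost is precision: fewer than 30 families contribute, and a family whose relapses were all found late without a prompt drops out of the depth analysis. The retention and engagement definitions need no change on this ground.

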Aim 2a. Evaluate UrApp engagement, use retention, and features used via user analytics and examine their relationships with UrApp efficacy with respect to primary and secondary outcomes.

Aim 2b. Explore user perceptions of UrApp features and barriers and facilitators of UrApp use via participant surveys and interviews.

Aim 3. Convene a committee of stakeholders of caregivers, clinicians, and mHealth engineers to collaboratively develop a user-centered UrApp enhanced nephrotic syndrome intervention program with the potential for wider implementation.

Aim 3a. Redesign as necessary the UrApp intervention to enhance UrApp use.

Aim 3b. Determine outcome measures most relevant to users and obtain user input on trial procedures to incorporate into the design of a future full-scale clinical trial.

Study Design

Overall design and organizational structure: 1:1 randomized trial of 1 year of UrApp use. The participants will be recruited from CHOA, Oregon Health and Science University (OHSU), University of Minnesota (UMn), and Medical University of South Carolina (MUSC). The trial will be followed by stakeholder engagement at CHOA to refine UrApp and plan a future large-scale trial.

CHOA will be led by the PI, [name], Assistant Professor of Pediatrics. [name] will oversee all study administration; ensure compliance with applicable laws; lead a collaborative agreement on a uniform study protocol across all four sites; prepare all research documents including data collection forms/database and consent/assent forms; provide training to site investigators and coordinators on the study protocol and data entry; and ensure site adherence with the protocol and appropriate data entry.

OHSU will be led by site PI, [name], Professor of Pediatrics. [name] will ensure that the study is conducted in compliance with applicable laws and regulations and institutional policies; collaboratively work with other investigators to agree on a uniform study protocol; oversee the recruitment of study participants and adherence with the protocol; and update [name] on the study progress and potential issues.

UMn will be led by site PI, [name], Associate Professor of Pediatrics and Division Director of Pediatric Nephrology at UMn. [name] will have the same responsibilities as other site PIs.

MUSC will be led by site PI, [name], Professor of Pediatrics and Chief of Pediatric Nephrology. [name] will have the same responsibilities as other site PIs.

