Analysis will follow the intention-to-treat principle to preserve the integrity of the randomization. Primary outcomes, adherence with urine monitoring and medications, will be analyzed via Chi-square test to compare the proportions of adherent patients in the UrApp vs SOC arms at 6 and 12 months. Results will be presented as group proportions and difference in proportions with associated 95% CIs. In an adjusted analysis using a generalized linear mixed model, we will examine the changes over time by testing the treatment arm (UrApp vs. SOC) by time (6 and 12 months) interaction. Models will include site as a random effect and adjust for any baseline characteristic differences between groups (including sex as a variable). Self-efficacy and QoL measures will be analyzed using linear mixed models. Models will include the effect of treatment (UrApp vs. SOC), time (baseline, 6 and 12 months), and the treatment by time interaction. Study center will be included as a covariate and/or a random effect. Post-hoc pairwise comparisons will be used to compare specific points in follow-up (6 and 12 months) to baseline within and across groups. Results will be presented as differences in means with associated 95% CIs. Baseline characteristics will be included in the models as covariates in an adjusted analysis. Three-way interactions will be utilized to explore the role of demographic characteristics and their association with treatment response. While not adequately powered to conduct a moderator analysis, effect sizes will be calculated by subgroup and will inform a future, full-scale study. Delayed relapse diagnosis and hospitalizations will be compared between the treatment arms using Poisson regression under the framework of generalized linear mixed models or generalized estimating equations to account for correlated data collected from the same individuals. Baseline characteristics will be included in the models as co-variates. Analysis will be guided by [name], and carried out using SAS v.9.4 (Cary, N.C.).

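### Aim 2a is framed as relating app use to UrApp efficacy, but its unadjusted within-arm tests show only association, which baseline differences between families can produce without any app effect

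*Combined protocol and SAP*

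**What the plan says.** All references are to the Combined protocol and SAP.

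- **Target.** Section 2, Goals/Aims, and the Aim 2a heading under Study Design both undertake to take the app-use measures and "examine their relationships with UrApp efficacy with respect to primary and secondary outcomes". Aim 2 as a whole is meant to find what influences the app's effectiveness.
- **Data.** Use measures come from the app's analytics, so they exist only for the UrApp arm (n=30). One split is defined as "adequate engagement as accessing UrApp at least two times per week during the first 3 months".
- **Analysis.** Aim 2a, Procedures and analysis: "The relationship between user behavior and primary and secondary outcomes (detailed under Aim 1) will be assessed via Chi-square test/Fisher's exact test or t-tests", with Wilcoxon rank-sum as the alternative. It names no covariate, baseline value or SOC comparison, and does not say whether follow-up levels or changes are compared.
- **Outcome timing.** Section 2, Measures/Materials: "Outcome measures will be collected at 6 and 12 months via caregiver surveys, medical chart review, and urine protein logs".
- **Baseline data.** The same section states: "Baseline self-efficacy and QoL will be assessed by surveys". The Section 3 schedule and the Section 4 baseline visit add the medication and urine-testing adherence surveys.
- **Contrast with Aim 1.** For self-efficacy and QoL, the Aim 1 analysis states: "Models will include the effect of treatment (UrApp vs. SOC), time (baseline, 6 and 12 months), and the treatment by time interaction". Those models serve the UrApp versus SOC comparison; nothing carries them over to Aim 2a.

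**The concern.** Efficacy is a contrast with SOC. The Aim 2a tests have a different null: that the outcome does not differ by how much a family uses the app. Families choose how much they use it. Caregivers who begin more confident, or already adherent, may both open the app more and report better outcomes later. The groups would then differ even if the app did nothing.

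The plan brings baseline values into the randomized comparison, where design already protects against confounding, and omits them from the non-randomized one, where they are needed.

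The stake is the use made of the result. Under Aim 3, trial results on efficacy and process evaluation go to the stakeholder committee, which plans the app's redesign and the full-scale trial. A use-outcome link described in terms of efficacy could steer that work toward raising use when it may only mark families who were already doing well.

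**Working it through.** **1. Plan's own figure.** The documents give no power or error rate for Aim 2a. The one stated figure, 82% power for urine monitoring in Aim 1, reproduces: pooled two-sided Z-test, 24 per arm (30 less 20%), 55% versus 90%, exact binomial enumeration, 0.8196. It is not in dispute. From it come n=30, and n=24 after drop-out, for the UrApp arm.

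**2. Model with no app effect.** Baseline score B, latent use U and follow-up score Y are standard normal, with corr(B,U)=r and corr(B,Y)=rho. Given B, use has no effect on Y. A family is engaged if U falls in the top fraction p. The values of r, rho and p are assumptions.

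**3. Hand approximation, p=0.5, n=30.**

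- Gap in mean Y, engaged minus not engaged: r × rho × k, where k = 0.3989/(0.5 × 0.5) = 1.596.
- Within-group SD: √(1 − gap² × 0.25).
- Noncentrality: (gap/SD) × √(30 × 0.25) = (gap/SD) × 2.739. Reject when |t| exceeds 2.048 on 28 df.

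Example with r=0.5, rho=0.7: gap = 0.35 × 1.596 = 0.559; SD = √(1 − 0.078) = 0.960; noncentrality = 0.582 × 2.739 = 1.59; rejection about 34%.

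**4. Approximation beside simulation, n=30.** The last column adds B as a covariate.

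| r | rho | Gap (SD) | Approx. | Simulated t-test, 50% / 60% engaged | Adjusted, 50% engaged |
|---|---|---|---|---|---|
| 0 | 0.6 | 0 | 5.0% | 5.1% / – | 5.1% |
| 0.3 | 0.5 | 0.239 | 9.8% | 9.4% / 9.7% | 4.5% |
| 0.3 | 0.7 | 0.335 | 14.7% | 14.0% / 14% | 5.5% |
| 0.5 | 0.5 | 0.399 | 19.0% | 17.9% / 19% | 5.0% |
| 0.5 | 0.7 | 0.559 | 33.7% | 32.7% / 32% | 4.5% |
| 0.7 | 0.7 | 0.782 | 61.3% | 60.1% / 59% | 5.0% |

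A further independent simulation gave about 9%, 31% and 58% for the (0.3, 0.5), (0.5, 0.7) and (0.7, 0.7) cells. With rho=0.5 and n=24-30, rejection is 5.3-6.2% at r=0.1 and 6.3-7.2% at r=0.2. At n=24 with 50% engaged and r from 0.3 to 0.7, it runs from 8.3% to 49.7%. Wilcoxon results are similar.

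**5. Change scores.** If outcomes are read as change from baseline, a t-test on Y − B still rejects 7% to 21% whenever r is 0.3 or more.

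**6. Binary adherence, n=30, 60% engaged.** The use-outcome latent correlation is r × rho: 0.5 × 0.5 = 0.25 to 0.5 × 0.7 = 0.35.

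| Adherent | Fisher (no correlation) | Uncorrected chi-square (no correlation) |
|---|---|---|
| 90% | 4.7-6.7% (1.2%) | 9.7-13.2% (3.0%) |
| 75% | 8.5-15.2% (2.8%) | 13.0-21.0% (5.1%) |

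**7. How far adjustment helps.** The return to about 5% in step 4 requires that B be the only confounder and be measured without error. With reliability 0.7, adjusted rejection at n=30 is about 9% (r=0.5, rho=0.7) and 13% (0.7, 0.7). With reliability 0.5 it is 13.6% and 24.2%. The planned self-efficacy measure has three adapted questions.

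**The case against.** **The tests are valid for what they test.** The analysis sentence speaks of a relationship. In the model above an association exists, so rejecting is not an error against the tests' own null. This stands. A reader might infer that the tests are invalid, or that they reject whenever confident families use the app more. Neither follows. The fault lies in tying the result to efficacy, and the rejection rate rises only as far as the correlations carry it.

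**The size is assumed.** Also right. The documents give neither the size nor the sign of r. At r of 0.2 or less the inflation is negligible. Less confident caregivers might lean on the app more; a real benefit could then be hidden, or heavier use could appear to go with worse outcomes.

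**Adjustment does not yield efficacy.** Also right. A reader might take an adjusted slope as a dose-response effect of the app. There is still no SOC contrast, and unmeasured traits remain.

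**The aim is formative, and the consequence is conjecture.** Aim 2a states no hypothesis, alpha or power, and no design decision is tied to an Aim 2a p-value. The randomized Aim 1 comparison is unaffected. This limits the seriousness, but does not excuse naming efficacy as the target with no caveat.

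**Outright replacement would lose families.** Eligibility starts at age 1, while parent PedsQL forms start at age 2 and child forms at age 5. Some families will have no baseline QoL score. This is why the adjusted analysis should be added and the unadjusted one kept.

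**Conclusion.** The point holds in limited form. Aim 2a names efficacy as its target, and the planned tests cannot address it; that mismatch stands whatever the correlations are. The statistical consequence depends on them: from almost none at r of 0.2 or less, through about 9% at r=0.3, rho=0.5, to 31% and 58% in the two strongest cells at n=30. Inflation is small for Fisher's test at adherence near 90%.

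The point applies to self-efficacy, QoL and medication adherence. Baseline adjustment does not resolve the overlap between opening the app and being counted as adherent to urine monitoring, and it does not deal with delayed relapse detection or hospitalizations.

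**What to change.** In Section 2, Aim 2a, Procedures and analysis:

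1. For self-efficacy and QoL, add as the main Aim 2a estimate a linear regression of the 6- and 12-month score on the use measure, with that outcome's baseline score as covariate.
2. For medication adherence, add a small-sample logistic regression (for example Firth) on the use measure with one baseline covariate: baseline medication adherence or baseline self-efficacy.
3. Report estimates with 95% CIs.
4. Keep the unadjusted tests as descriptive. This also retains families without a baseline QoL form.
5. State that the results are within-arm associations, not evidence that UrApp efficacy depends on use, and reword the Aim 2a heading and the Goals/Aims entry to match.

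The cost is wording plus one model degree of freedom in 24-30 families. No new survey or visit is needed. Residual confounding remains, which is why item 5 is needed alongside items 1 and 2.
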